2.4 Correlative Studies Background

Protein-based biomarkers in blood hold a great promise as diagnostic markers indicative of disease states and outcomes in clinical cancer management. In order to validate large sets of candidate markers in bio-banked sample collections, multiplexed and sensitive detection technologies with low sample consumption are required. Such technologies will not only be critical for the discovery of biomarker panels potentially leading to increased predictive power in diagnostics but may eventually enable early stage disease detection(21-22).

Most conventional immunoassays rely on a solid support for capture of the target protein and for the removal of excess secondary reporter antibody by washing. These sandwich assays' susceptibility to nonspecific binding of the secondary reporter to the surface limit their sensitivity. Also, any single non-cognate binding event by a detection antibody will give rise to a false positive signal. This is especially challenging when performing

multiplexed reactions with many detection antibodies thus requiring extensive and careful optimization through selection of particular antibody combinations in order to minimize non-specific cross reactivity(23-24).

We have developed a method of protein detection (proximity ligation assay) utilizing an antibody-based method of detection coupled with a qPCR amplification step (25). The assay consumes 1 µL of sample with low femto-molar sensitivity, five log linear range, and can be multi-plexed without cross-reactivity. The procedure typically relies upon a single polyclonal antibody batch for each target protein, simplifying affinity reagent creation for novel biomarker candidates.

Based upon our previous studies (26), we will measure plasma levels of the following proteins prior to initiating treatment and 3 months following SBRT as outlined in the protocol: VEGF, MIF, CTGF, IL-1alpha, IL-7, galectin-1, TNF-alpha, EpCAM, CEA, Adam8, CPA1, ErbB2, IGF-2, CA 19-9, SLPI, Ch3L, EGFR, Osteopontin, Mesothelin, CA-125. We hypothesize that biomarker profile from this group of proteins will be predictive of outcome in this group of pancreatic cancer patients with locally advanced disease.

Collection of specimens as outlined above will not be required from all participating institutions. Additional protein biomarkers may also be assessed.

3. PATIENT SELECTION

3.1 Inclusion Criteria

- Histologically confirmed adenocarcinoma of the pancreas.
- Determined unresectable by a pancreatic cancer surgeon or a multi-disciplinary or gastrointestinal oncology Tumor Board.
- Stable or better disease on re-staging scans following induction mFOLFIRINOX..
- Typically, pancreatic tumors must be less than 8.0 cm in greatest axial dimension at the time of treatment planning but final determination of eligibility will be based upon satisfying the radiation normal tissue constraints as specified below in section 6.1.3 Radiation Treatment Planning.
- No prior systemic therapy EXCEPT patients may be consented and enrolled if they have already started mFOLFIRINOX for up to four cycles.
- ECOG 0, 1, or 2 (see Appendix II).
- Patients must have acceptable organ and marrow function as defined below and within 30 days of eligibility confirmation:
 - leukocytes (WBC) $\geq 3,000/\mu\text{L}$
 - absolute neutrophil count (ANC) $\geq 1,500/\mu\text{L}$
 - platelets $\geq 50,000/\mu\text{L}$

- total bilirubin ≤ 1.5 X institutional upper limit of normal
 - AST(SGOT) / ALT(SGPT) ≤ 2.5 X institutional upper limit of normal
 - Creatinine not above the upper limit of normal institutional limits.
- Ability to understand and the willingness to sign an informed consent form.
 - Life expectancy > 6 months.

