5.2 Restaging Following mFOLFIRINOX

After induction chemotherapy (up to 4 cycles), patients will have a CT scan for re-staging. Re-staging scans should be scheduled within 2 weeks following completion of induction mFOLFIRINOX. To allow for scheduling complications, outside sites may perform the simulation (SIM) scan during the final cycle of chemotherapy up to 4 weeks prior to start of treatment. If the subjects are randomized to the SBRT arm and the SIM was more than 4 weeks prior to treatment start date, a re-SIM will be performed to ensure that the plan is still appropriate for tumor treatment.

- If there is radiological or clinical evidence of disease progression, patient will not continue with the randomized portion of this study, but should be treated according to treating physician's discretion. (Based upon the study by Conroy *et al*, the progression-free survival at 3 months is estimated to be 75%; therefore the number of patients evaluated for the protocol and ultimately enrolled will be adjusted accordingly.) These patients will continue to be followed as part of the study.
- If a patient has radiologically responding or stable disease, s/he may proceed with randomization as described in the following section. Patients may undergo surgical resection at any time if clinically appropriate after surgical evaluation.

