5.3 Randomization to +/- SBRT

Participating centers will submit re-staging scan reports (and images as requested) within 5 business days of the scan's final report date to Stanford, along with documentation of consent. These should be sent in a secure electronic mail message or fax to the PI ([name]) and Clinical Research Coordinator [name] with subject line: "SECURE: STUDY PATIENT FOR RANDOMIZATION". Stanford research staff will randomize the subject by participating site and within the next business day, will send an electronic message to the PI and Research Coordinator from the participating center with the outcome and instructed treatment plan.

Randomization will be done with R software, a randomized block design. It will be performed by a Stanford Statistician or the Stanford study coordinator who will maintain a password-protected list and assign patients to the treatment arms as each patient is enrolled at each institution. Randomization Arm will be confirmed by two coordinators prior to electronic notification and written documentation (Note to File) of the treating physician and outside research coordinators.

Subjects **randomized to SBRT** are allowed up to an 8-week break between induction chemotherapy and radiation treatments.

Subjects **randomized to mFOLFIRINOX** can continue directly with that treatment. Any breaks between mFOLFIRINOX cycles will be determined by the treating Medical Oncologist and are permitted for up to 8 weeks.

If a subject exceeds the allowable 8-week break between treatments, s/he may continue treatment “off protocol” and as recommended by the treating Medical Oncologist or according to local standard of care. These subjects will be followed for overall survival and progression-free survival. Subsequent data analysis will be performed on an intention-to-treat basis.

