6.1.3 Radiation Treatment Planning

- 1) When available, an FDG-PET scan is preferred for treatment planning purposes and will be acquired on a flat table top whenever possible with the

- same immobilization devices used for the treatment planning CT simulation.
- 2) An SBRT treatment plan will be developed using Eclipse™, Multi-Plan™ or Pinnacle™ based on tumor geometry and location at each institution. Institutional standards for radiation quality assurance and radiation delivery will be utilized.
 - 3) The final tumor volume (GTV) as identified on the treatment planning CT, will be defined by the attending radiation oncologist after reviewing the diagnostic CT, respiratory-correlated 4D-CT scan, pancreas protocol CT, and the FDG-PET/CT scan. These scans will be used to define the ITV (internal target volume). The final PTV (planning treatment volume) expansion will consist of an additional 2-3 mm of margin expansion, except if the margin results in expansion into the duodenum or stomach. In these cases, margin expansion is allowed to be non-uniform. The dose will be prescribed to the isodose line that completely surrounds the PTV. It is recommended that either 6-12 co-planer fields or 2-4 conformal arcs be used in the radiation treatment plan.
 - 4) When fiducials are used, contours of the fiducials used for target localization will be generated on the applicable image sets, to be used for patient setup on treatment.
 - 5) Radiation dose to the adjacent normal tissue will be minimized and these dose constraints should be met:
 - **Duodenum:** $D_{max} < 40$ Gy, $V_{35} < 1cc$, $V_{30} < 10cc$, $V_{20} < 30cc$. V_{35} , V_{30} , and V_{20} are defined as the volume receiving 35, 30, and 20 Gy, respectively. The duodenum (duo@PTV) as defined for these dosing parameters includes entire duodenum on the same axial plane as the PTV and duodenum 1 cm above and 1 cm below the PTV. The remainder of the normal tissues will be limited as follows:
 - **Liver** (excluding tumor): 50% should be limited to < 12 Gy
 - **Kidney:** Combined volume for both should have 75% < 12 Gy
 - **Stomach:** $D_{max} < 40$ Gy, $V_{35} < 1cc$, $V_{30} < 10cc$, $V_{20} < 30cc$. (no more than 1 cc of stomach can receive > 35 Gy)
 - **Spinal Cord:** no more than 1cc can receive > 15 Gy
 - 6) No more than 1cc of the PTV can receive $> 130\%$ of the prescription dose.
 - 7) Greater than 90% of the PTV should receive 100% of the prescription dose.

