 - 8) If above constraints cannot be met, 100% of the GTV must receive at least 33 Gy and a request for a minor deviation should be submitted. If this constraint still cannot be met, the patient should be withdrawn from the study and treated according to local standard of care.

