Appendix IV

Eligibility Checklist

Protocol Information

Title	Pancreatic Cancer Radiotherapy Study Group (PanCRS) Trial: A Randomized Phase III Study Evaluating Modified FOLFIRINOX (mFFX) with or without Stereotactic Body Radiotherapy (SBRT) in the Treatment of Locally Advanced Pancreatic Cancer
Number	27492
Principal Investigator	[name]

Subject Information

Subject Name: _____
Study ID: _____
Gender:  Male  Female

Inclusion/Exclusion Criteria

Inclusion Criteria (From IRB approved protocol)	Yes	No	Supporting Documentation*
1. Histologically confirmed adenocarcinoma of the pancreas			
2. Induction mFOLFIRINOX up to 4 cycles			
3. Stable or better disease on re-staging scans			
4. Determined unresectable by a pancreatic cancer surgeon or a multi-disciplinary or gastrointestinal oncology Tumor Board			
5. Typically, pancreatic tumors must be < 8.0 cm in greatest axial dimension at time of treatment planning but final determination of eligibility will be based upon satisfying the radiation normal tissue constraints as specified in protocol (Section 6.1.3 - Radiation Treatment Planning).			
6. ECOG 0, 1, or 2			

7. Acceptable organ and marrow function as defined below and within 30 days of eligibility confirmation: a. Leukocytes $\geq 3,000/\mu\text{L}$ b. ANC $\geq 1,500/\mu\text{L}$ c. Platelets $\geq 50,000/\mu\text{L}$ d. Total bilirubin $\leq 1.5 \times$ institutional upper limits of normal e. AST (SGOT)/ALT (SGPT) $\leq 2.5 \times$ institutional upper limit of normal f. Creatinine not above the upper limit of normal institutional limits			
8. Ability to understand and the willingness to sign a written informed consent document			
9. Life expectancy >6 months			

Exclusion Criteria (From IRB approved protocol)	Yes	No	Supporting Documentation*
1. Children / Age <18 years			
2. Metastatic disease			

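### Final eligibility depends on a dose plan that is not required before randomization; where planning comes later, only SBRT-arm patients can fail, and those withdrawn lose PFS follow-up

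*Combined protocol and SAP*

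**What the plan says.** Section 3.1 gives a usual tumor size limit of 8.0 cm and then states that "final determination of eligibility will be based upon satisfying the radiation normal tissue constraints as specified below in section 6.1.3 Radiation Treatment Planning". The synopsis repeats this, and item 5 of the Appendix IV checklist carries the same test: "final determination of eligibility will be based upon satisfying the radiation normal tissue constraints as specified in protocol".

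Section 6.1.3 item 5 opens the list with "Radiation dose to the adjacent normal tissue will be minimized and these dose constraints should be met" and sets maximum-dose and dose-volume limits for duodenum, stomach, liver, kidney and cord. Items 6 and 7 add limits on target hot spots and coverage. Item 8 is the fallback when the limits are missed: "100% of the GTV must receive at least 33 Gy and a request for a minor deviation should be submitted". If that also fails, "the patient should be withdrawn from the study and treated according to local standard of care".

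On timing, Section 4.2 has the checklist approved before enrollment. Section 5.3 lists what is sent for randomization: "Participating centers will submit re-staging scan reports (and images as requested" and a record of consent. The Section 14 calendar puts seed placement and simulation in the SBRT column, after randomization. Section 5.2 adds that "outside sites may perform the simulation (SIM) scan during the final cycle of chemotherapy up to 4 weeks prior to start of treatment".

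On consequences, Section 7.5 follows withdrawn patients for overall survival only. Section 11.4.1 groups deviations that affect eligibility with the serious or major ones. Section 17.2 defines ITT as every randomized patient.

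**The concern.** A criterion that decides eligibility should be answerable for every patient before the arm is known. This one needs a dose distribution, and the plan does not require one until after assignment, and then only in the SBRT arm. Where a site plans after randomization, a tumor that cannot be planned is discovered only if the patient drew SBRT. The same tumor in the control arm is never tested.

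What follows is also one-armed. Patients who miss the fallback are withdrawn, and the general rule for withdrawn patients stops progression follow-up. PFS is the primary endpoint, so its data would be lost selectively in the experimental arm, from patients whose tumors were hardest to treat. Patients who meet the fallback stay on study, but the protocol does not say clearly whether they are eligible, a minor deviation or a major one.

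**Working it through.** **Step 1. Can the criterion be judged without a plan?** No. Maximum dose, V35, V30 and V20 are read from a computed dose distribution on a simulation scan. The 8.0 cm guide can be judged on diagnostic imaging, but it is only the usual rule; Section 3.1 gives the final word to the constraints.

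**Step 2. Is a plan required before assignment?** No.
- Section 5.3 lists no plan or dosimetry.
- The calendar places simulation after randomization, in the SBRT column.
- Section 4.2 links fiducial implantation to patients randomized to SBRT, and Section 6.1.2 prefers simulation at least 5 days after fiducials.
- Sections 5.2, 6.1 and 6.1.1 allow earlier simulation or seed placement. These are permissions, and Section 5.2 covers the scan, not a finished plan.
- Nothing requires a plan for a control patient.

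**Step 3. What happens to a patient whose plan misses the constraints?**
- Fallback met: the patient continues under a minor deviation (6.1.3 item 8), yet a deviation affecting eligibility is serious or major (11.4.1).
- Fallback missed: the patient is withdrawn (6.1.3 item 8) and followed for overall survival only (7.5). By contrast, Sections 5.3 and 7.1 keep PFS follow-up for patients who exceed the 8-week break.
- Section 15.1.5 censors PFS at the last progression evaluation. The first required post-treatment scan is at 3 months, so a patient withdrawn at planning may have no evaluation after randomization. Such a patient is formally in ITT but contributes no PFS time.
- Section 15.1.5 also counts death as a PFS event. If deaths found in survival follow-up are used, PFS would be recorded at death, later than the unrecorded progression. The plan does not say which applies.

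**Step 4. The plan's own figures.** Inputs from Sections 17.3.2 and 17.5.2: 86 per arm, medians 6 and 10.2 months, 60 months of accrual, 12 months minimum follow-up, two-sided 0.05. With λ = ln 2/median, P(event) = 1 − [exp(−12λ) − exp(−72λ)]/(60λ).
- Control: 86 × 0.964 = 82.9. SBRT: 86 × 0.893 = 76.8. Total 159.7 (plan: 83 + 77 = 160).
- HR = 6/10.2 = 0.588. Schoenfeld: Φ(√160 × |ln 0.588|/2 − 1.96) = Φ(1.396) = 91.9%. Freedman gives 90.6%, Lachin–Foulkes 90.3%, and log-rank simulation 91.3%. The stated 91% reproduces.

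**Step 5. Illustration of size.** The documents give no failure rate and no prognosis for unplannable tumors. Assumed: 5–20% unplannable. Null columns: the same share in both arms, with 1.5–2 times the hazard of the rest, and PFS lost only in the SBRT arm. Power columns: affected SBRT-arm patients have the control hazard. Each scenario has 4,000 log-rank simulations with 86 per arm. HRs are one-step log-rank estimates (0.577 in the run with no failures, true value 0.588).

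| Share | Null HR, censored at 1 month (rejection rate) | Null HR, no PFS time (rejection rate) | Power, censored at 1 month | Power, kept in ITT with PFS |
|---|---|---|---|---|
| 5% | 0.977–0.987 (4.5–5.2%) | 0.975–0.984 (5.6–5.7%) | 89.5% | 88.5% |
| 10% | 0.953–0.977 (5.6–6.3%) | 0.951–0.964 (5.6–5.9%) | 88.9% | 86.2% |
| 20% | 0.918–0.945 (6.6–7.9%) | 0.899–0.932 (7.0–10.0%) | 86.2% | 78.4% |

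The Monte Carlo standard error of a 5% rejection rate is √(0.05 × 0.95/4000) = 0.34 points, so rates near 5.6% are hardly distinguishable from nominal.

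**The case against.** The strongest defence is that Section 17.2 keeps every randomized patient in ITT and that nothing excludes a patient for missing the constraints. That stands. A reader might infer that the primary analysis drops ineligible SBRT-arm patients, but the text does not say so. The only route to harm in ITT is loss of progression data after withdrawal.

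Four other inferences also go further than the documents.
- **Control patients can never fail the criterion.** Checklist item 5 is asked of everyone, and the checklist includes the re-staging result. Nominally the criterion covers both arms. What is missing is any plan on which a control patient's answer could rest.
- **Item 8 contradicts or overrides Section 3.1.** Item 8 belongs to the section that 3.1 imports, and item 5 says only that the limits should be met. One can read 3.1 as including the fallback. The unresolved conflict is with Section 11.4.1 over the patient's status.
- **The criterion distorts the per-protocol set.** Section 17.2 defines that set by completed treatment. An SBRT patient with no deliverable plan leaves it however 3.1 is worded.
- **These patients would be logged as ineligible patients randomized (deviation code 13).** No passage links that code to plan failure.

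Finally, the size is wholly assumed. That is correct, and the table shows direction and plausible order only.

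**Conclusion.** The point holds in this form: final eligibility rests on a plan-derived test, no plan is required before assignment, and where planning follows randomization only SBRT-arm patients can be found to fail. Those who also miss the fallback are withdrawn, and Section 7.5 then ends their progression follow-up, so primary-endpoint data are lost in one arm. Following the plan as written produces this, so it is more than a missing detail.

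ITT prevents exclusion bias only if these patients stay in it and their PFS is still collected. The text is certain; the frequency is unknown. Under the stated assumptions the shift is slight at 5%. At 20% the null HR is about 0.90 to 0.95, favouring SBRT, and this needs unplannable tumors to have a worse prognosis. The figures do not show that the trial's result will be biased.

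**What to change.** 1. Have SBRT feasibility judged and recorded for every patient before randomization, on imaging already obtained, and add that record to the Section 5.3 submission. The sponsor sets the clinical criterion; this review does not choose a size or dose rule.
2. State that missing the 6.1.3 constraints after randomization is a treatment-delivery outcome and not ineligibility, and that the patient stays in the assigned arm for ITT with PFS follow-up continued. The per-protocol set stays as Section 17.2 defines it.
3. Reconcile Sections 3.1, 6.1.3 item 8, 7.5, 11.4.1 and 14 and Appendix IV, with the synopsis, so that a patient whose plan misses the constraints has one status throughout.

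The cost is protocol and checklist wording, one recorded judgment per patient, and continued scans for a few patients. The statistical downside is dilution, because SBRT-arm patients who prove unplannable remain in ITT. It is small if few are affected, but power would fall to 78.4% at an assumed 20%, which is a further reason to judge feasibility before assignment.

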3.2 Exclusion Criteria

- Children/Age<18 (rarely occurs in this age group)
- Metastatic disease.
- Prior radiotherapy to the upper abdomen/liver.
- Patients who have received chemotherapy for pancreatic cancer, other than up to 4 cycles of mFOLFIRINOX as noted above.
- Uncontrolled illness including, but not limited to, ongoing or active infection (or infections requiring systemic antibiotic treatment), symptomatic congestive heart failure, unstable angina pectoris, cardiac arrhythmia, or psychiatric illness/social situations that would limit compliance with study requirements.
- Any concurrent malignancy other than non-melanoma skin cancer, non-invasive bladder cancer, or carcinoma in situ of the cervix. Patients with a previous malignancy without evidence of disease for > 5 years will be allowed to enter the trial.
- Pregnant and breastfeeding women are excluded; as well as women of child-bearing potential who are unwilling or unable to use an acceptable method of birth control (hormonal or barrier method of birth control; abstinence) to avoid pregnancy for the duration of the study. Male subjects must also agree to use effective contraception for the same period as above. Should a woman become pregnant or suspect she is pregnant while participating in this study, she should inform her treating physician immediately.
- Women who are not post-menopausal (as defined in Appendix III) and have a positive urine or serum pregnancy test or refuse to take a pregnancy test.

4. STUDY ENROLLMENT

4.1 General Guidelines

Subjects will be identified per the recommendation of referring surgeons, Combined Modality Tumor Board or equivalent combined modality assessment, or through self-referral and the advice of their attending physician. No advertisement will be used to recruit

subjects.

See Diagram in Section 16.2 for phases and workflow of study.

4.2 Registration and Enrollment

Research staff at each participating center will ensure that all requisite procedures and tests have been performed and complete an Eligibility Checklist (See Appendix IV) to submit to Stanford research staff for review. Stanford research staff will contact the center regarding approval of patient's study participation, and the patient may then be enrolled and registered.

The participating center will register subjects according to their institutional guidelines and as per this protocol.

In some patients, an optional additional core biopsy may be obtained for research purposes if consent is provided by the patient. It may be done at the time of fiducial implantation (in patients randomized to SBRT) as described in Section 12.1, Laboratory Correlative Studies; or as a separate procedure (for patients randomized to mFFX alone). This option will vary by participating institution.

